Study investigators will audio record the return of results sessions, whether in-person or over the phone, so that GCs at HA can check for minor, major, and high-risk errors in communication of the WGS findings that will be corrected, appropriately. (see appendix 13 for the audio recording process)

(1) Results (ROR) Recordings

Prior to the WGS result disclosure participants will be reminded that the interaction will be recorded using a digital audio recorder, and their GG account username/password will be needed post-ROR for completion of the GCOS and FACToR measures. They will be reminded that the purpose of the recording is to help the study team understand how the results are described and what questions and topics come up during the discussion. Participants will be reminded that the recordings will only be used by the SouthSeq study and no identifiable information will be shared outside of the study team.

Participants are given an opportunity to opt-out of the recording, but their results would have to be delivered by a GC. This can cause a delay if the participant is scheduled to have results delivered by a trained healthcare provider. Participants will not be given a copy of the recording. However, if they self-select to record the session on their own device that is permissible.

The GC or physician conducting the results disclosure will begin by verbally introducing the people attending the return of results session. This introduction/preamble will be scripted (appendix 13), the audio recording is begun and the family ID is stated clearly on the recording, as well as the name of the clinician doing the disclosure.

The parents/caregivers are counseled on the genetic test results, and when the interaction is finished, the recording is stopped. The digital recording file is uploaded in Genome Gateway to the designated HudsonAlpha GC (based on site) by the site study coordinator within 72 hours (3 business days) for positive or VUS results and within 7 business days for negative results. Errors will not be tracked within the GC arm, but only within the trained healthcare provider arm. Below are the HudsonAlpha GCs assigned to each clinical site:

Birmingham, AL (UAB): [name], MS, CGC

Jackson, MS (UMMC): [name], MS, CGC

Baton Rouge, LA (BR): [name], MS, CGC

New Orleans, LA(LSU): [name], MS, CGC

University of Louisville (UL): [name], MS, CGC

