Providers who will be disclosing results to participants as part of the clinical trial must attend the in-person training or participate in a “make-up” training, consisting of watching recordings of didactic portions of the training and a virtual workshop/conference call with a HudsonAlpha GC to cover the discussion, hands-on, and role-play portions of the training.

The family-friendly report that will be developed for each case (by a HA genetic counselor) will also provide just-in-time education to the providers about a specific result and what it means – and provide a road map for topics to discuss with the participant.

If providers have questions regarding the study and specific results, they will be instructed to reach out to a HudsonAlpha GC for assistance, rather than their own site-specific GC. This will allow for centralized tracking and management of questions and issues that come up across all the sites and limit compromises to the clinical trial.

3.e.4 Study Outcomes

The **primary hypothesis for this non-inferiority trial** is that there will be no clinically relevant difference in parental empowerment, as a measure of health-related quality of life between parents in the Experimental (trained healthcare provider) arm when compared to the Standard of Care (genetics providers) arm. The primary study outcome is parental **empowerment** (McAllister *et. al.*, 2011, PMID: 21255005), which will be measured at the WGS return of results (ROR) visit, ~3 months after enrollment (see appendix 7 for survey measures). To ensure completion of the primary outcome, parents or caregivers will be asked to complete the parental empowerment measure on-site (or over the phone) immediately after the return of results. The remaining measures included in the ROR visit will be available to complete via Genome Gateway at their convenience.

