ENR: Enrollment * Post WGS (whole genome sequencing); [†]Genetic Counseling Outcome Scale; [‡]Parental Perceptions of Uncertainties in Genomic Sequencing; [◊]The Feelings About genomic Testing Results [#]Genetic Counseling Satisfaction Scale; [§]Genetic Knowledge Assessment; [¶]Visual Analog Scale ^Δ Parental Personal Utility Scale; [◊]Subjective Numeracy Scale; [¶]National Health and Nutrition Examination Survey; [□]12-Item Short Form Survey; [¶]Medical Outcomes Study. In green, primary analyses. ^{**} GCOS and FACToR need to be completed in-person (or over the phone) immediately after ROR delivery before leaving session.

(1) Primary Outcomes

The main outcome to be assessed as part of this randomized controlled clinical trial will be **parental empowerment** as measured at the main time point for our study (i.e., immediately after the ROR visit). Parental empowerment will be measured using the validated Genome Counseling Outcome Scale (GCOS), which contains 24, 7-point Likert type items, with higher scores representing greater empowerment. The GCOS-24 that we are using for our participants measures patient reported outcomes (PRO) and has been proposed as a measure to evaluate routine clinical genetics services (McAllister *et. al.*, 2011, PMID: 21255005).

(2) Secondary Outcomes

To avoid survey fatigue and undue emotional burden, not all secondary or exploratory outcome instruments will be administered at each time point. The secondary outcomes assessed at the main time point (WGS ROR visit) for this study are: **personal utility** and **parental uncertainty**. Personal utility will be assessed using the parental personal utility scale (PrU). Parental uncertainty will be assessed using the Parental Perceptions of Uncertainties in Genomic Sequencing (PUGS).

(3) Exploratory Outcomes

Genetic knowledge and background genetic education will be addressed using the Genetic Knowledge Assessment (Schmidlen et. al., 2016, PMID: 26306685). The Genetic Knowledge Assessment (GKA) is a questionnaire containing 15 true/false knowledge items and 4 education background questions. In addition, we will assess parental subjective understanding of their child's results by asking respondents to rate their agreement.

(4) Covariates

Beyond the primary, secondary, and exploratory outcomes described above, a schedule of other data being collected for use in various analyses is provided in table 2.

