Complete the Questionnaires assigned to you by selecting “My Surveys”

HUDSONALPHA
INSTITUTE FOR BIOTECHNOLOGY

Complete the Questionnaires assigned to you by clicking on a “Current Questionnaire” being sure to **reference the Study ID Number**

[figure not shown]
- Research nurse will complete assigned surveys in Genome Gateway.
 - These surveys are focused on phenotypes, previous genetic testing, prenatal testing (if known) and the enrollment process. (see screenshot steps below)
 - This information will be accessible to the analysis team at HudsonAlpha.

Select the patient from the list. Click Assign on Return of Results Baseline Questionnaire

[figure not shown]
Select due date from the calendar. Click Assign.
Reminders will be preset at defined times

- The due date should be up to ROR (roughly 2 ½ months for baseline). All subsequent surveys will be set 1-month from the day you assign the survey.
- The due date reminders will be automatically preselected for you (2-day before, 7-days before, and 14-days before)
- Research nurse will ship samples to the Clinical Services Laboratory at HudsonAlpha and submit them for sequencing via online portal.
- The research nurse will upload the W9 (needed for payment) and the informed consent form to GG.
 - Screenshots highlighting how to upload documents are below.

Uploading Documents to Genome Gateway

Navigate to “Files” from the homepage

To upload a file, select patient, then click “+”

Write message to send with file below

Choose File no file selected

1. Click "Choose File" - a finder window will open
 2. Select file (any file type) from correct location on computer
 3. Click "Choose"
 4. Click "Upload" to send it to the patient

**A message can be included with the file in the text box

- Forms/survey measures completed at enrollment
 - Informed Consent Form (ICF)- (paper form uploaded to Genome Gateway; hard copy kept in study binder)
 - W9 form (paper form uploaded to GG; hard copy kept in study binder until clinical trial team informs the coordinator to destroy- 7 years)
 - Participant Enrollment Survey
 - Sociodemographic in GG
 - Genetic Counseling Outcome Scale (GCOS)
 - Genetic Knowledge Assessment (GKA)
 - Visual Analog Scale (VAS)- Child's Health
 - Parental Perceptions of Uncertainties in Genomic Sequencing (PUGS)
 - Health Literacy
 - Subjective Numeracy Scale (SNS)
 - 12-item Short Form Survey (SF-12)
 - Medical Outcomes Survey (MOS)

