Errors will be tracked within GG utilizing a participant-specific questionnaire that is assigned to the GC completing the review. This questionnaire will ask about the length of the recording, the name of the clinician doing the disclosure, and whether any errors were noted as well as the contents of the error. The questionnaire will ask separately about each error type (safety error, major error, minor error). See Figure 2 for a breakdown of error types.

Figure 2. Types of Genetic Test Reporting Errors

Minor Errors

In the case of a minor error, these errors will be tracked internally but no intervention will be made.

Definition: Errors in the non-critical details that have little expected impact on participant understanding, decision-making and management.

Examples:

- Saying the participant “has the gene” instead of saying the participant “has a gene mutation”
- Saying the gene is on the incorrect chromosome
- Terminology misuse - heterozygous versus homozygous

Major Errors

In the case of a major error, the disclosing healthcare provider will receive a message from the reviewing GC clarifying the error and recommending he/she follow-up with the participant to convey corrected/additional information. The clinician is expected to correct the misconception both with the patient and any documentation they did clinically at their site. If the clinician asks for assistance or does not feel comfortable addressing the error, the genetic counselor will be responsive to those requests. If a participant reaches out to HA with questions, [name] will address concerns, but the disclosing healthcare provider is expected to be the one to have direct patient contact and a patient relationship.

Definition: Errors in the critical content that have a significant expected impact on participant understanding, decision-making, and/or management.

Examples:

- Wrong recurrence risk (i.e. stating recurrence risk is 25% when it is actually <1%)
- Confusion regarding etiology (*de novo*, parental carrier status)
- False reassurance (i.e. counseling that WGS will provide a concrete answer as to participant’s life expectancy)
 - Negative results and the misconception that it rules out genetic etiology (explicit statements)
- Misunderstanding of pathogenicity/penetrance
 - Likelihood of actual development of features/severity
- Incorrect understanding of a VUS (saying it is highly unlikely to be the cause/is nothing to worry about; or saying it is definitely the cause)

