Form	Visit Administered	Instructions	Location
Informed Consent	Enrollment Visit	Participant/s reads consent. Study staff obtaining consent should sign, date, and time stamp	Paper, uploaded to Genome Gateway
Screening/Decliner Survey	Enrollment Visit	Completed by research nurse or study coordinator	Electronic Copy
Enrollment Survey	Enrollment Visit	Completed by parent or caregiver after study enrollment	Genome Gateway
Return of Results (ROR) Survey (In-clinic and At-home surveys)	GCOS and FACToR at ROR Visit; Additional measures after visit	Complete primary outcome measure (GCOS) and FACToR measure immediately after ROR, additional measures can be completed at participant's convenience	Genome Gateway
1-month post-ROR Survey	Complete 1-month post ROR	Complete survey online using GG	Genome Gateway
4-month post-ROR Survey	Complete 4-months post ROR	Complete survey online using GG	Genome Gateway
4-month plus 2 weeks post-ROR Survey	Complete 4-months plus 2 weeks post-ROR	Complete survey online using GG	Genome Gateway

User roles (researchers, providers, patients/participants and administrators) with secure log-in will be defined. The following information will be tracked: current user, database accessed, date, and time and the application will be stopped automatically after 15 minutes of user inactivity requiring a fresh log-in. All data will be collected via the questionnaires in Genome Gateway. The clinical trial study coordinator, clinical trial project manager and statistician will review all data collected weekly. This will help ensure all electronic forms are being completed correctly, are intact, and have been entered into system correctly.

3.j.2 General Instructions for Completing Forms

All data recorded in Genome Gateway will be maintained according to the International Council for Harmonization of Technical Requirements for Pharmaceuticals for Human Use (ICH) Good Clinical Practice (GCP) guidelines. Instructions for completing the questionnaires to ensure quality and consistency in data collection are below.

3.j.3 Retention of Study Documentation

Investigators will adhere to rigorous requirements and will retain copies of all paper (e.g. informed consent), electronic forms, and all other study documents for a period of no less than 7 years. Each site will maintain all documents, and at the close of the study UAB will retain all site documents.

3.j.4 Administrative Forms

Table 4. Administrative Forms

Form	Description	Location

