11. ***Considering your child's medical condition, please rank the degree to which you agree with the following statements:**

	Strongly Disagree	Disagree	Somewhat Disagree	Neutral	Somewhat Agree	Agree	Strongly Agree
I am clear in my own mind why my family has enrolled in SouthSeq.							
I can explain what the condition means to people in my family who may need to know.							
I understand the impact of the condition on my child(ren)/any child I may have.							
When I think about the condition in my family, I get upset.							
I don't know where to go to get the medical help I/my family need (s).							
I can see that good things have come from having this condition in my family.							
I can control how this condition affects my family.							
I feel positive about the future.							
I am able to cope with having this condition in my family.							
I don't know what could be gained from each of the options available to me.							
Having this condition in my family makes me feel anxious.							
I don't know if this condition could affect my other relatives (brothers, sisters, aunts, uncles, cousins).							

In relation to the condition in my family, nothing I decide will change the future for my children/any children I might have.							
I understand the reasons why my child's doctor referred my family to SouthSeq							
I know how to get the non-medical help I/my family need(s) (e.g. educational, financial, social support).							
I can explain what the condition means to people outside my family who may need to know (e.g. teachers, social workers).							
I don't know what I can do to change how this condition affects me/my children.							
I don't know who else in my family might be at risk for this condition.							
I am hopeful that my child(ren) can look forward to a rewarding family life.							
I am able to make plans for the future.							
I feel guilty because I (might have) passed this condition on to my children.							
I am powerless to do anything about this condition in my family.							
I understand what concerns led to my referral to SouthSeq							
I can make decisions about the condition that may change my child(ren)'s future/the							

future of any child(ren) I may have.						
---	--	--	--	--	--	--

12. *The following questions ask about how you, as a parent, felt after receiving your child's genetic test results. Please indicate how much you had each specific feeling in the past week by choosing the one answer for each question.

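### PUGS and PrU are declared outcomes immediately after the results visit but may be answered up to a month later, while FACToR, a covariate with a past-week recall window, takes the in-session slot

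*Combined protocol and SAP*

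**What the plan says.** Section 3.e.5 (1) takes the primary outcome, GCOS, "as measured at the main time point for our study (i.e., immediately after the ROR visit". Section 3.e.5 (2) places the two secondary outcomes, PrU and PUGS, at the same point: "The secondary outcomes assessed at the main time point (WGS ROR visit) for this study are".

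The operating instructions differ. Section 3.e.4 has GCOS completed at once and then says: "The remaining measures included in the ROR visit will be available to complete via Genome Gateway at their convenience". Table 3 requires GCOS and FACToR immediately after ROR, while "additional measures can be completed at participant's convenience". On due dates, section 3.f.2 (1) says: "All subsequent surveys will be set 1-month from the day you assign the survey". Section 3.f.3 also gives a one-month deadline for questionnaires. Appendix 15 has the At-Home Survey assigned while the disclosure is in progress. Its script tells families that they will be asked to do both surveys straight after the conversation.

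FACToR must be finished before the family leaves (3.e.5 (4), 3.f.2 (2)); section 3.f.2 (2) justifies this by calling it an important covariate. Its stem in Appendix 7.2, question 12, reads: "Please indicate how much you had each specific feeling in the past week by choosing the one answer for each question".

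On error review, section 3.e.2 (1) says: "Errors will not be tracked within the GC arm, but only within the trained healthcare provider arm". For a major error, section 3.g.1 has the reviewing counselor message the provider, "clarifying the error and recommending he/she follow-up with the participant to convey corrected/additional information".

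**The concern.** The two secondary non-inferiority comparisons are meant to show how parents stand immediately after hearing the result from one type of clinician or the other. As the surveys are set up, a PUGS or PrU score can be given minutes after disclosure or about a month later. In that interval a provider-arm family may be recontacted to correct a major error that a genetic counselor found on the recording. Counselor-arm recordings are not checked for errors, so no such correction can follow there. A late provider-arm score may therefore reflect disclosure plus correction, while a late counselor-arm score reflects disclosure alone.

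The supervised slot meanwhile goes to FACToR, which is neither a primary nor a secondary outcome. Asked minutes after disclosure about the past week, it covers a period that lies almost wholly before the result. The 1- and 4-month forms use the same stem at a time when the whole week follows the result, so the ROR score is not comparable with the later ones.

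**Working it through.** **1. Permitted window.** GCOS and FACToR: same session, or by phone within 72 hours if the coordinator is unavailable (Appendix 15). PUGS and PrU: day 0 to about day 30. The documents do not say that the survey closes then. The SAP sets no completion window and no analysis by time since ROR.

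**2. When a correction can arrive.** Recordings are uploaded within 3 business days (positive or uncertain results) or 7 (negative) under section 3.e.2 (1). Review follows within 72 business hours or a week (Appendices 13 and 15). I assume that review time runs from upload, that 72 business hours means 3 business days, and that visits fall on weekdays.
- Positive or uncertain: 3 + 3 = 6 business days, which is 8 to 10 calendar days at the latest.
- Negative: 7 business days span 9 to 11 calendar days; adding 7 gives day 16 to 18 at the latest.

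The provider's recontact comes after that, with no deadline stated. The preset reminders are 14, 7 and 2 days before the due date: 30 − 14 = day 16, 30 − 7 = day 23, 30 − 2 = day 28. A parent who answers on a reminder therefore does so about when, or after, a correction may have been made. All three reminders also fall outside the rule in section 3.e.5 of three reminders within two weeks of the visit.

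**3. Is anyone missing?** Per-instrument numbers are not given. With equal arms assumed, n per arm = (SD₁² + SD₂²)/SE², where SE = (bound − difference)/t. For PrU:
- difference 78.40 − 73.93 = 4.47; half-width 10.13 − 4.47 = 5.66; SE = 5.66/1.972 = 2.87
- n = (20.51² + 19.86²)/2.87² ≈ 99 per arm
- check: (10 − 4.47)/2.87 = 1.93, one-sided p = 0.0277, which reproduces the SAP.

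The same formula gives about 96 per arm for GCOS and 100 for PUGS. The take-home instruments show no visible loss of responders against GCOS. The issue is spread in completion time, not missing data.

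**4. Could timing change a verdict?** Let a share q of the provider arm answer after a correction that moves their mean score by δ. The shares below are illustrations; the documents report none.
- *PrU* failed. If δ is positive (correction flatters the provider arm), removing it raises the bound to 10.13 + qδ, and the failure stands. Only a correction that lowered PrU could have caused the failure: 0.13/0.05 = 2.6 points at q = 5%, or 0.13/0.10 = 1.3 points at q = 10%.
- *PUGS* passed with 3.5 − 1.22 = 2.28 points to spare. Overturning it needs 2.28/0.05 = 45.6 points at 5%, or 2.28/0.10 = 22.8 at 10%. Eight items scored 1 to 5, if summed, span 8 × 4 = 32 points. The first figure is impossible and the second implausible.

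**5. FACToR in the analysis.** The SAP uses unadjusted two-sample tests with no covariate, and FACToR is measured after randomization. No stated analysis needs it in session. Section 3.e.5 says the most important measures come first, yet Appendix 7.2 puts FACToR (question 12) ahead of PUGS (13) and PrU (14).

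**6. Length.** Standard form: PUGS 8 + PrU 17 = 25 items against FACToR 14, so 11 more. Deceased-proband form (Appendix 7.2A): no PUGS, PrU 6 against FACToR 7, so one fewer.

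**The case against.** Several counter-arguments have weight.

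- Families are asked to complete both surveys right away, and those who do so answer before any correction. This stands, but it is a request. It sits beside instructions that allow the parent's convenience and a month.
- A corrected score needs a major error, an actual recontact (the counselor's message recommends it, although section 3.g.1 also expects the clinician to correct the misconception), and a survey still unanswered. The share could be small. This also stands; the documents give no figure.
- Correction may be part of the experimental strategy. The provider training slides present recording and error tracking as safety nets. That is a fair reading of the intervention, but it does not fit an outcome fixed immediately after the visit, before a correction can happen.
- Survey burden straight after a difficult conversation is a real reason to keep the session short, and section 3.e.5 (2) raises it. It argues for choosing the in-session instruments carefully, not for preferring FACToR to the tested outcomes.

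A reader might infer that timing decided the PrU result, because it missed by only 0.13 points. The documents do not support this: the mechanism that would favor the provider arm works against such a reversal. A reader might also infer that FACToR cannot be answered in session. It can, since the stem asks about feelings after receiving the result; the recall window simply fits poorly.

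**Conclusion.** The declared time point and the operating rules for PUGS and PrU do not agree, and the gap allows a corrective exposure that exists in one arm only. That is a weakness in how both secondary comparisons can be interpreted. Its size is unknown, because neither completion times nor correction rates are reported. No change to either reported combined verdict is shown: PrU would still fail if corrections flattered the provider arm, and PUGS is too far inside its margin at the shares tried. These statements rest on equal arms, a summed PUGS score and illustrative shares of 5% and 10%. The in-session FACToR score should not be treated as a baseline for the 1- and 4-month scores. The change below is a cheap improvement and worth making.

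**What to change.** For families still to be surveyed, place PUGS and PrU directly after GCOS in the In-Clinic Survey. Move FACToR to the At-Home Survey, opened about 7 days after ROR, so that the past week is the week since disclosure. GCOS stays first and protected. The cost is form reassignment in Genome Gateway, an IRB amendment, 11 more in-session items on the standard form, and possibly lower FACToR completion. FACToR at day 7 could itself follow a correction, which matters less because the SAP does not test it.

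Reassigning forms cannot alter results already in the SAP. For families already surveyed:

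- Report time from ROR to completion of PUGS and PrU, by arm.
- Add a sensitivity analysis that applies the same short completion window in both arms, beside the all-completers result. Within 72 hours of ROR is one choice, since the phone in-clinic survey already has that allowance. It limits but does not exclude earlier corrections. It also selects on a post-randomization variable, so it should not replace the main result.
- Do not exclude families because they had a corrective contact. Only the provider arm can have one, so the filter would remove error cases from one arm.

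Reconcile sections 3.e.4, 3.e.5, 3.f.2 (1), Table 3 and the Appendix 15 script on when PUGS and PrU are due. Also reconcile the 1-month list in section 3.f.2 (3), which has neither PUGS nor PrU, with Appendix 7.3, which has both. As Appendix 7.3 stands, a late ROR response can coincide with the 1-month form asking the same items.
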